## 1. GLOSSARY OF ABBREVIATIONS

CRF case report form

CSR clinical study report

CTCAE Common Terminology Criteria for Adverse Events

ECG electrocardiogram

EOS end of study

EOT end of treatment

HU hydroxyurea

MedDRA Medical Dictionary for Regulatory Activities

NCI National Cancer Institute

OLE open-label extension

RBC red blood cell

SAE serious adverse event
SAP statistical analysis plan

SCD sickle cell diseaseSOC System Organ Class

TEAE treatment-emergent adverse event

VOC vaso-occlusive crisis

WHO World Health Organization

#### 2. INTRODUCTION

The objective of Study GBT440-034 (C5341022) is to assess the long-term safety and treatment effect of voxelotor in participants with sickle cell disease (SCD) who have completed treatment in Study GBT440-031.

This statistical analysis plan (SAP) provides details of the planned analyses and statistical methods for Study GBT440-034 final clinical study report (CSR). Where this document differs from the high-level analysis plan described in the study protocol, the methodology described in this SAP is considered the latest and supersedes the corresponding section(s) in the protocol.

# 2.1. Study Design

Study GBT440-034 is a multicenter, global, open-label extension (OLE) study available to participants who were previously enrolled and treated in Study GBT440-031. Participants must meet the entry criteria for this study to be eligible for enrollment.

All participants enrolled in GBT440-034, regardless of treatment received in the parent study GBT440-031 (i.e., placebo, voxelotor 900 mg, or voxelotor 1500 mg), receive treatment with voxelotor 1500 mg once daily (the highest dose deemed safe for continued assessment based on GBT440-031).

All participants in Study GBT440-034 have scheduled study visits with assessments at Day 1, Week 12, Week 24, and Week 48, and then every 24 weeks thereafter. Participants who were treated with placebo or voxelotor 900 mg in Study GBT440-031 have additional study visits with assessments at Week 4 and Week 8.

Participants may receive voxelotor in GBT440-034 as long as they continue to receive clinical benefit which outweighs risk as determined by the Investigator and/or until the participant has access to voxelotor from an alternative source (i.e., commercialization or through a managed access program).

Additional details and background information are provided in the study protocol.

# 2.2. Study Endpoints

#### **2.2.1.** Safety

Safety endpoints include adverse events, clinical laboratory tests, physical examinations, and other clinical measures.

## 2.2.2. Sickle Cell Disease (SCD)-Related Complications

Frequency of SCD-related complications of long-term dosing with voxelotor. SCD-related complications include adverse events with preferred terms of acute chest syndrome, hepatic sequestration, leg ulcers, osteonecrosis, pneumonia, priapism, pulmonary hypertension, retinopathy, scleral icterus, sickle cell anaemia with crisis, splenic sequestration, and stroke.

#### 2.2.3. Treatment Effect (Durability of Hematologic Effect)

Hemolytic anemia as measured by hematological laboratory parameters (e.g., hemoglobin, reticulocytes, and unconjugated bilirubin).

# 2.3. Determination of Sample Size

The sample size for this study will not exceed the total enrollment of the parent study GBT440-031 (i.e., will not exceed 274 participants).

## 2.4. Analysis Timing

The final analysis will be based on complete data from the study, and performed after all enrolled participants have completed the study or discontinued early (i.e., last participant's last visit has occurred), and all corresponding data have been entered into the database, reviewed, and verified and the database is locked.

Prior to the final study analysis, interim data from this open-label extension study were summarized as necessary (e.g., interim safety data summarized to support regulatory applications and health authority requests). The data included for the interim analyses were dependent on the purpose of the regulatory submission. When performed, interim analyses were descriptive with no formal hypothesis testing performed.

## 3. GENERAL CONSIDERATIONS

# 3.1. Definitions and Terminology

#### Baseline Value

Baseline value is defined as the last available value (including from Week 72, End of Treatment [EOT], or End of Study [EOS] visits in the parent study GBT440-031) collected on or prior to first dose in GBT440-034, and will be used for summary of change from GBT440-034 baseline analyses, as appropriate. If multiple records exist in the GBT440-034 database, all laboratory records prior to treatment initiation in GBT440-034 will be averaged and used as the baseline value.

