3.1.1.3. Treatment Effect

Hemolytic anemia as measured by hematological laboratory parameters (eg, hemoglobin, reticulocytes and unconjugated bilirubin).

3.1.2. **Design**

This open label extension (OLE), multi-center study will be conducted at approximately 100 clinical sites globally and will be available to eligible participants from study GBT440-031.

The study will enroll participants from GBT440-031 under any of the following conditions:

- Participant has completed 72 weeks of treatment regardless of dose selection for GBT440-031
- Dose selection has occurred for GBT440-031 and participant is on the nonselected dose on GBT440-031
- GBT440-031 study interim data analysis and/or study modifications have occurred
- GBT440-031 study has completed

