4.1. Subject Inclusion Criteria

- Male or female study participants with SCD who participated and received study treatment in GBT440-031.
 - Note: Participants in GBT440-031 who discontinued study drug due to an AE, but who remained on study may be eligible for treatment in this study provided the AE does not pose a risk for treatment with voxelotor.
- Females of child-bearing potential are required to have a negative urine pregnancy test prior to dosing on Day 1.
- Female participants of child-bearing potential must use highly effective methods of contraception to 30 days after the last dose of study drug. Male participants must use barrier methods of contraception to 30 days after the last dose of study drug.
- 4. Participant has provided written informed consent or assent (the ICF must be reviewed and signed by each participant; in the case of pediatric participants, both the consent of the participant's legal representative or legal guardian, and the participant's assent must be obtained).

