5. TREATMENT OF SUBJECTS

Participants who complete 72 weeks of treatment on GBT440-031, regardless of a dose selection for GBT440-031, will receive voxelotor at the highest dose (either 900 or 1500-mg) deemed safe for continued assessment on the GBT440-031 study by the Data Safety Monitoring Board (DSMB).

Once a dose is selected for study GBT440-031, all GBT440-031 participants on the nonselected dose will be eligible to enroll into this OLE study at the selected dose. All participants already enrolled in this OLE study at the time of the dose selection will be administered the selected dose at their next scheduled assessment.

Participants may be eligible to enroll in this OLE study prior to GBT440-031 study completion based on interim data results and/or subsequent study modifications on GBT440-031. If this occurs, sites will be notified which participants are eligible.

When study GBT440-031 has completed, participants will be eligible to enroll in this study.

If a participant was on a reduced dose of voxelotor due to an AE in GBT440-031 or on this study prior to a dose selection on GBT440-031, dosing in this study may be continued at the reduced dose if deemed clinically appropriate by the Investigator. The original dose may be resumed if deemed clinically appropriate by the Investigator.

Participants may receive study drug as long as they continue to receive clinical benefit which outweighs risk as determined by the Investigator and/or until the participant has access to voxelotor from an alternative source (i.e., commercialization or through a managed access program).

The EOS visit can occur any time after participants obtains commercial voxelotor for participants who complete study per protocol. Participants should remain on study drug until EOS visit is completed.

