15. APPENDICES

Appendix 1. Schedule of assessments

Assessments			Tre	eatment I	Period					End of Studyi
Study Day(s)	Day 1ª	W4* ± 5 days	W8* ± 5 days	W12 ± 5 days	W24 ± 10 days	W36 ± 10 days	W48 ± 10 days	Q12 Wks ± 10 days	Q24 Wks ± 10 days	
Informed Consent/Assent	X							unjs	unjs	
Eligibility Assessment	X									
Medical History	X									
Physical Examination b	X	X	X	X	X		X		X	X
Vital Signs ^c	X	X	X	X	X		X			X
Adverse Events	X	X	X	X	X		X		X	X
Concomitant Medications	X	X	X	X	X		X		X	X
Hematology/Chemistry analyzed by Central Laboratory (US and Europe only) ^d	X	X	X	X	X		X			X
Hematology/Chemistry analyzed by Local Laboratory (ex-US and ex-Europe only) ^{d, e}	Xª	X	X	X	X		X		X f	Х
Exploratory Laboratory CCI (US and Europe Only)	X			X	X		X			
Urine Pregnancy Test ^g	X	X	X	X	X		X		X	X
Drug Dispensing and Accountability ^h	X			X	X	X	X	X	X	Х

Assessments		Treatment Period							End of Studyi	
Study Day(s)	Day	W4*	W8*	W12	W24	W36	W48	Q12	Q24	
	1ª	± 5	± 5	± 5	± 10	± 10	± 10	Wks	Wks	
		days	days	days	days	days	days	± 10	± 10	
								days	days	

Amendment 3

Abbreviations: Q = every; W = week; Wks = weeks

- * Participants from GBT440-031 who received GBT440 900 mg or placebo, or who received voxelotor for less than 12 weeks will have additional assessments at Week 4 and Week 8.
- a. Eligibility assessments will be determined on Day 1 prior to dosing. If labs were done for GBT440-031 or this study within 7 days of Day 1, they do not need to be repeated on Day 1.
- Abbreviated Physical Exam which includes: general appearance, examination of eyes, skin, cardiovascular and respiratory systems, an abdominal examination and a symptom directed examination.
- c. Vital signs (heart rate [HR], blood pressure [BP]) will be collected after a participant has rested for at least 5 minutes in the seated or supine position. A repeated measurement of HR and BP will be taken if the first reading is outside the normal range and deemed clinically significant.
- d. Hematology assessments will include: red blood cell (RBC), hematocrit (Hct), hemoglobin (Hb), platelets, white blood cell (WBC), we reticulocytes, absolute reticulocytes, RBC distribution width (RDW), mean corpuscular volume (MCV) and mean corpuscular hemoglobin concentration (MCHC). After Week 48, hematology assessments should only be performed per standard of care.

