# **4.2.** Safety Population

The safety population includes all enrolled participants who received treatment with study drug (voxelotor) during Study GBT440-034.

The safety population will be the primary analysis population for this study.

Analyses will be presented for overall population, and by prior treatment group (i.e., placebo, voxelotor 900 mg, and voxelotor 1500 mg) based on treatment received in the parent study GBT440-031, as appropriate.

<sup>a Including Week 72, End of Treatment, or End of Study laboratory values collected in Study GBT440-031.

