#### 5. STATISTICAL METHODS

All statistical analyses will be descriptive in nature; no formal statistical tests are planned.

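### The prior-voxelotor groups can mix on-drug and off-drug baselines, so the mean change from the GBT440-034 baseline can blunt a loss of durability and, at a large off-drug share, hide it

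*SAP*

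**What the plan says.** **Baseline.** SAP 3.1 states: "Baseline value is defined as the last available value (including from Week 72, End of Treatment [EOT], or End of Study [EOS] visits" in GBT440-031, provided the sample was taken on or before the first GBT440-034 dose. Drug status at that sample is not part of the definition, and no maximum sample age is given. Protocol Appendix 1, footnote a, lets the Day 1 laboratory draw be skipped under one condition: "If labs were done for GBT440-031 or this study within 7 days of Day 1".

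**Who can enter.** The note to the first inclusion criterion in Protocol 4.1 reads: "Participants in GBT440-031 who discontinued study drug due to an AE, but who remained on study may be eligible", as long as the event poses no risk for voxelotor treatment. Entry is also open after the parent study ends. Protocol 5 says: "When study GBT440-031 has completed, participants will be eligible to enroll in this study". Neither document limits the time between the last parent dose and the first extension dose.

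**Grouping.** SAP 4.2 presents results overall and by prior placebo, 900 mg or 1500 mg, "based on treatment received in the parent study GBT440-031, as appropriate". Protocol 8.7 likewise groups by parent treatment only.

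**Durability analysis.** SAP 5.5 summarises haemoglobin, indirect bilirubin and reticulocytes as values and as changes from the GBT440-034 baseline, through Week 48. Protocol 6.1 and 8.1.1.3 also call for change from the GBT440-031 pre-dose baseline. SAP 5.5 does not carry this, and SAP 2 says that the SAP prevails where the two differ.

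**Dose.** SAP 2.1 places all participants on 1500 mg, whatever they received in the parent study.

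**The concern.** In a participant who goes straight from 1500 mg in the parent study to 1500 mg in the extension, a change near zero means that the effect has been kept, and a fall is the signal of interest. In a participant whose baseline was taken off drug, a rise shows treatment being started again, as in the prior-placebo group. The two changes answer different questions, and the SAP averages them under one label.

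The error has a direction. Off-drug baselines push the group mean change up, which works against seeing a fall among those treated throughout. The SAP plans no count of participants who re-started and no summary of their gap. A reader of the durability table could not tell whether the effect is trivial or important.

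**Working it through.** The plan states no effect size, power or off-drug share for this analysis, so there is no figure of its own to reproduce. The check is mixture arithmetic.

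**Inputs**
- G: haemoglobin lost on stopping and regained on re-starting. Protocol 1.3.2 reports an improvement of more than 1 g/dL over placebo at 24 weeks. I use 1.0 g/dL, with an assumed range of 0.8 to 1.2.
- p: share of a prior-voxelotor group whose baseline sample was off drug. Not in the documents; 5% to 30% shown.
- L: true loss of effect by the extension visit. Assumed values 0.10, 0.25 and 0.50 g/dL.

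**Model 1: the loss applies to everyone.** Continuing participants change by −L and re-starters by G − L.

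Mean change = (1 − p)(−L) + p(G − L) = pG − L.

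The upward shift is pG. With G = 1.0 it is +0.05, +0.10, +0.20 and +0.30 g/dL at p = 5%, 10%, 20% and 30%.

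| True loss L (g/dL) | p = 5% | p = 10% | p = 20% | p = 30% | p that gives zero (L/G) |
|---|---|---|---|---|---|
| 0.10 | −0.05 | 0.00 | +0.10 | +0.20 | 10% |
| 0.25 | −0.20 | −0.15 | −0.05 | +0.05 | 25% |
| 0.50 | −0.45 | −0.40 | −0.30 | −0.20 | 50% |

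Check at L = 0.25 and p = 25%: 0.75 × (−0.25) + 0.25 × 0.75 = 0.

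Over G = 0.8 to 1.2, the share that hides the loss completely is 8–13%, 21–31% and 42–63% for the three losses.

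**Model 2: re-starters regain all of G and do not wane.**

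Mean change = pG − (1 − p)L, which is zero at p = L/(L + G).

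With G = 1.0 these shares are 0.10/1.10 = 9%, 0.25/1.25 = 20% and 0.50/1.50 = 33%. Check at L = 0.25 and p = 20%: 0.8 × (−0.25) + 0.2 × 1.0 = 0.

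**What other displays would show (Model 1, G = 1.0)**
- Continuing participants alone, from the GBT440-034 baseline: −0.10, −0.25 and −0.50 g/dL, which is the true loss.
- Whole group, from the parent pre-dose baseline: G − L = +0.90, +0.75 and +0.50 g/dL, whatever p is.

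**The case against.** **The off-drug share may be small.** The documents lean towards direct rollover. Protocol 2 frames the objective around people who finished treatment in the parent study, and Protocol 1.7 speaks of continued access. Protocol 7.2.2.1 even allows for a first extension dose before the parent end-of-treatment visit is complete. The one explicit off-drug route is the adverse-event note in Protocol 4.1. Entry after parent completion sets no maximum gap, but that does not show that gaps occurred. This stands: at p = 5% the shift is about 0.05 g/dL, and a 0.25 g/dL loss would still show as −0.20.

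**Sample age.** A reader might infer that accepting an old parent sample inflates the change. The documents do not support that. Appendix 1 requires a Day 1 draw unless there is a result within 7 days, so an old value would be used only if that draw is missing. If that old value was taken on drug, the baseline is high and no re-start gain appears. The upward shift needs a sample that was itself off drug.

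**The analysis is descriptive.** The SAP says: "All statistical analyses will be descriptive in nature; no formal statistical tests are planned". No decision rule can wrongly declare the effect maintained, and values by visit are shown alongside changes. That limits the consequence, but the values by visit carry the same mixture.

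**Restoring the parent pre-dose baseline would expose a loss.** It would, as the arithmetic shows, and it should be done. It would still leave the GBT440-034 change table mixed, and the protocol plans that table too.

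**Conclusion.** The mechanism follows from the documents: applied as written, the SAP averages retained and re-started effect within the prior-voxelotor groups whenever off-drug entrants are present. The shift in mean haemoglobin change is p × G, about +0.05 g/dL at p = 5% and +0.20 g/dL at p = 20%. A 0.25 g/dL loss is blunted at small p and disappears only at about p = 25%, or 20% if re-starters show no waning.

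These figures assume that G is about 1 g/dL and that the off-drug baselines reflect full loss of effect. Both p and L are assumptions.

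A reader might infer that the durability table will conceal waning. The documents do not support that, because they give no off-drug share and mostly describe direct rollover. What they support is that the table can understate a loss by an amount the reader has no means to judge. The prior-placebo group is unaffected. Prior 1500 mg is the clean case, because prior-900 mg participants also change dose. The change should be made, but it is not critical.

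**What to change.** **SAP 3.1.** Derive two intervals for each prior-voxelotor participant: (a) days from last parent voxelotor dose to the baseline sample, and (b) days from last parent dose to first GBT440-034 dose. Class a participant as continuing only if both are within a short limit fixed before the analysis; otherwise class as re-started. Both are needed, because someone with an on-drug end-of-treatment sample and then a long break would pass (a) alone. The 7 days in Appendix 1 footnote a should not be taken as the source of the limit, since that window runs to extension Day 1 and not from the last parent dose.

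**SAP 4.2 and 5.5.** Show the prior-voxelotor groups split by this flag, with counts and gap lengths. Read durability from the continuing prior-1500 mg row. Show continuing prior-900 mg participants separately, because SAP 2.1 puts everyone on 1500 mg and their expected change is not zero.

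**Alongside this,** restore change from the GBT440-031 pre-dose baseline (Protocol 6.1 and 8.1.1.3). The split complements that analysis and does not replace it.

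**Cost.** SAP wording and a flag derived from dates already held across the two studies. SAP 3.1 already draws on parent-study laboratory values. No visit, sample or treatment changes. The re-started rows may be small and imprecise, but their count alone would tell the reader how much the mixing matters.

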#### Prior Study Drug

Prior study drug (or prior study treatment) refers to the study drug (i.e., placebo, voxelotor 900 mg, or voxelotor 1500 mg) received during the parent study GBT440-031. All participants receive open-label voxelotor as study drug during GBT440-034.

#### Study Day

Study Day is defined relative to the date of GBT440-034 informed consent.

For study assessments or events that occur on or after the date of informed consent, study day is calculated as:

Study Day = Event Date - Informed Consent Date + 1.

#### Study Year

Study Year is defined relative to the date of GBT440-034 informed consent, and refers to study year within Study GBT440-034 only. Study year is calculated as:

Study Year = ceiling(Study Day/365.25).

#### Treatment Day

Treatment Day is defined relative to the date of GBT440-034 first dose.

For study assessments that occur on or after the date of first dose, treatment day is calculated as:

Treatment Day = Assessment Date - First Dose Date + 1.

For study assessments that occur before the date of first dose, treatment day is calculated as:

Treatment Day = Event Date - First Dose Date.

### Treatment-Emergent Adverse Event

Treatment-emergent adverse events (TEAEs) are defined as adverse events with onset on or after the date of informed consent until 28 days after last dose of study drug. Note: For this study, informed consent date is used (rather than first dose date) as the majority of participants were previously treated with voxelotor in the parent study GBT440-031.

## **Study Completion**

Completion of study is specified on the EOS case report form (CRF). Participants are considered to have completed the study if they end study participation to transition to voxelotor from an alternative source (i.e., commercialization or through a managed access program). Participants who end study participation for any other reason (e.g., adverse event, withdrawal of consent, lost to follow-up, study terminated by sponsor) are considered to have discontinued the study early.

#### **Treatment Completion**

Completion of treatment is specified on the EOT CRF. Participants are considered to have completed treatment if they end study drug treatment to transition to voxelotor from an alternative source. Participants who end study treatment for any other reason (e.g., adverse event, withdrawal of consent, lost to follow-up, study terminated by sponsor) are considered to have discontinued study treatment early.

#### 3.2. Visit Windows

For summaries by timepoint (e.g., laboratory values and vital signs), analysis visit windows will be used to classify assessments based on the actual treatment day of the measurement regardless of the original nominal visit label. This includes assessments collected at Unscheduled or EOS visits. Target study days, the protocol-specified study day windows, and the analysis visit windows are shown in Table 1.

**Table 1:** Analysis Windows

Timepoint	Target Study Day (relative to first dose)	Visit Window per Protocol (treatment days)	Window for Statistical Analysis (treatment days)
Baseline	1		Last value a taken on or prior to date of first dose in GBT440-034
Week 4	28	[23, 33]	[2, 42]
Week 8	56	[51, 61]	[43, 70]

Timepoint	Target Study Day (relative to first dose)	Visit Window per Protocol (treatment days)	Window for Statistical Analysis (treatment days)		
Week 12	84	[79, 89]	[71, 126]		
Week 24	168	[158, 178]	[127, 252]		
Week 48	336	[326, 346]	[253, 420]		
Week 72	504	[494, 514]	[421, 588]		
Week 96	672	[662, 682]	[589, 756]		
Week 120	840	[830, 850]	[757, 924]		
Week 144	1008	[998, 1018]	[925, 1092]		
Week 168	1176	[1166, 1186]	[1093, 1260]		
Week 192	1344	[1334, 1354]	[1261, 1428]		
	< Continues with 24-week intervals >				

Note: If multiple measurements fall within the statistical analysis window, the average of the measurements will be used.

Note that per the protocol Schedule of Assessments, laboratory assessments and vital signs are collected at visits up to Week 48. After Week 48, laboratory assessments are collected per standard of care for clinical management with the following exception: for participants enrolled outside of the US and Europe, hemoglobin and clinical measures of hemolysis (% reticulocytes, absolute reticulocytes, and bilirubin [total, direct, and indirect]) are collected after Week 48 at 24-week intervals (see Section 5.4.3).

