4.3. Subject Withdrawal Criteria

Participants will be informed that they are free to withdraw from the study at any time and for any reason. If a participant withdraws from this study, the date and reason for withdrawal will be documented on the case report form (CRF).

Participants may be discontinued from study treatment for any of the following reasons:

Adverse event

- Use of a prohibited therapy (Section 5.5.3)
- Withdrawal of consent/assent
- Discretion of the Investigator
- Participant is lost to follow-up
- Participant is noncompliant
- Pregnancy

The End of Study (EOS) visit should be conducted within 28-35 days after last dose of study drug for participants who withdraw from the study early.

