- e. Serum chemistries will include: Alanine aminotransferase (ALT), alkaline phosphatase (ALK), aspartate aminotransferase (AST), bicarbonate, BUN, creatinine, LDH, sodium, potassium, bilirubin (total, direct, and indirect). After Week 48, serum chemistries should only be performed per standard of care.
- f. After Week 48 (for participants enrolled outside of the United States and Europe), laboratory values for measures of hemolysis such as hemoglobin, % reticulocytes, absolute reticulocytes, and bilirubin (total, direct, and indirect) will be collected every 24 weeks.
- g. If a urine pregnancy test is positive, the result must be confirmed per local standard of care (eg. ultrasound or serum pregnancy test).
- h. Voxelotor will be dispensed in 12-week (~90 day) intervals with instruction to participants to return any used/unused bottles to clinic.
- The End of Study (EOS) visit should be conducted within 28-35 days after last dose of study drug for participants who withdraw from the study early.

The EOS visit can occur any time after participants obtains commercial voxelotor for participants who complete study per protocol. Participants who complete study per protocol should remain on study drug until EOS visit is completed.

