# 5.5. Treatment Effect (Durability of Hematologic Effect)

Descriptive summaries of hemoglobin, indirect bilirubin, % reticulocytes, and absolute reticulocytes for all participants at GBT440-034 baseline and each evaluation post baseline through Week 48, as well as changes from baseline over time, will be provided. Laboratory assessments within 8 weeks post RBC transfusion, for any reason, will be imputed by the last laboratory value prior to the transfusion.

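### The durability summary counts early withdrawers' End of Study samples, taken 28-35 days off drug, as Week 4-48 values (low impact; optional, cheap improvement)

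*SAP*

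**What the plan says.** SAP 3.2 classifies by-timepoint data by actual treatment day and ignores the nominal visit label. It adds: "This includes assessments collected at Unscheduled or EOS visits". The note to its Table 1 says: "If multiple measurements fall within the statistical analysis window, the average of the measurements will be used". Treatment day depends on the first dose only: "Treatment Day = Assessment Date - First Dose Date + 1". It therefore carries no information on whether the participant was still taking drug.

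SAP 5.5 summarizes hemoglobin, indirect bilirubin and both reticulocyte measures "for all participants at GBT440-034 baseline and each evaluation post baseline through Week 48". Its only data-handling rule concerns transfusion: "Laboratory assessments within 8 weeks post RBC transfusion, for any reason, will be imputed by the last laboratory value prior to the transfusion".

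Protocol 4.3 says the EOS visit "should be conducted within 28-35 days after last dose of study drug for participants who withdraw from the study early", and Appendix 1 repeats this. The Appendix 1 schedule marks hematology and chemistry at EOS for both the central and the local laboratory rows. Completers are treated differently: "Participants who complete study per protocol should remain on study drug until EOS visit is completed".

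**The concern.** Protocol 8.1.1.3 describes the hematology analysis as showing trends while participants are on treatment. A hemoglobin value taken a month after stopping does not show whether the effect lasts on treatment. Under the SAP rule it nevertheless enters a visit mean with nothing to mark it as off drug. A reader who sees a lower Week 48 mean could not tell loss of effect on treatment from the consequence of stopping.

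Elsewhere the SAP does set limits. Vaso-occlusive crises (5.4.2) and transfusions (5.4.3) are counted up to the last dose date, and the maximum-grade laboratory shifts (5.3.3) use 28 days after discontinuation. None of these limits applies to the 5.5 means.

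**Working it through.** **1. The plan's own windows.** Each upper bound in SAP Table 1 is the midpoint of adjacent target days: (28+56)/2 = 42, (56+84)/2 = 70, (84+168)/2 = 126, (168+336)/2 = 252, (336+504)/2 = 420. Each lower bound is the previous upper bound plus 1, starting at day 2. All five windows are reproduced, and there are no gaps between them.

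**2. Which withdrawals reach which window.** With L the treatment day of the last dose, the EOS day is L+28 to L+35. A window [a, b] can be reached for L from max(1, a−35) to b−28. The EOS value can be the only scheduled value in the window if L also falls before the protocol visit window opens (days 23, 51, 79, 158, 326).

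| Timepoint | Window | L that can reach it | L where EOS can be the only scheduled value |
|---|---|---|---|
| Week 4 | [2, 42] | 1-14 | 1-14 |
| Week 8 | [43, 70] | 8-42 | 8-42 |
| Week 12 | [71, 126] | 36-98 | 36-78 |
| Week 24 | [127, 252] | 92-224 | 92-157 |
| Week 48 | [253, 420] | 218-392 | 218-325 |

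Example: last dose on day 300, EOS on days 328-335. The sample is labelled Week 48, although the participant was off drug by the day 336 target. Any on-schedule EOS sample after a last dose on days 1-385 enters one of the five timepoints, because 385+35 = 420.

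**3. Size.** The inputs below are assumptions, because the documents do not give them:
- withdrawal hazard 0.1, 0.2 or 0.4 per year (exponential);
- EOS attendance 25-75%, since withdrawn consent and loss to follow-up are among the listed reasons for stopping;
- EOS gap uniform on 28-35 days;
- one on-drug value at the target day if the participant is still treated;
- on-drug minus off-drug hemoglobin difference D = 0.55-1.1 g/dL, that is, 50-100% loss of an assumed 1.1 (Protocol 1.3.2 says only that the increase exceeded 1 g/dL).

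The effective off-drug weight is w = (share with an off-drug value only + 0.5 × share averaged with an on-drug value), among participants with a value. If withdrawers respond on drug as continuers do, baseline cancels and the visit mean falls by w × D.

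Week 48, hazard 0.2, 75% attendance: 4.63% off-drug only and 2.06% averaged, so w = 4.63 + 0.5 × 2.06 = 5.66%. The shift is 0.0566 × 1.1 = 0.062 g/dL.

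| Timepoint | w at 25% / 75% attendance, hazard 0.1 | hazard 0.2 | hazard 0.4 | Shift over the whole range (g/dL) |
|---|---|---|---|---|
| Week 48 | 0.97 / 2.87% | 1.95 / 5.66% | 3.92 / 11.05% | 0.005-0.12 |
| Week 24 | 0.68 / 2.02% | 1.36 / 4.00% | 2.72 / 7.85% | 0.004-0.09 |
| Week 12 | 0.34 / 1.03% | 0.69 / 2.05% | 1.39 / 4.06% | 0.002-0.045 |
| Week 8 | 0.19 / 0.58% | 0.39 / 1.16% | 0.79 / 2.32% | 0.001-0.026 |
| Week 4 | 0.07 / 0.22% | 0.15 / 0.43% | 0.29 / 0.88% | under 0.001-0.010 |

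The lower end of each range is the smallest w × 0.55, and the upper end is the largest w × 1.1. The Week 4 and Week 8 rows apply to participants who have those visits scheduled.

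**4. Late EOS samples.** Footnotes d and e of Appendix 1 leave hematology and chemistry after Week 48 to standard of care, while the EOS column is still marked. If EOS samples after day 346 (the close of the Week 48 visit window) are not drawn, w at hazard 0.2 and 75% attendance falls from 5.66% to 3.85%. That is about one third less.

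**5. Not modelled.** The transfusion rule would replace some EOS values. If 20% were replaced by on-drug values, the shifts would be multiplied by 0.8. Unscheduled on-drug samples in the same window would dilute the shift further.

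**The case against.** The strongest reply is that this is a stated choice. SAP 3.2 includes EOS samples in so many words, SAP 5.5 covers all participants, and the SAP supersedes the protocol where they differ. On this view the limits on crises and transfusions govern event counts and are only a loose precedent for laboratory means. This stands in part: the window rule is deliberate. But it is a general rule for all by-timepoint summaries, and nothing in 5.5 shows that its effect on a durability display was considered.

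A second reply is that the size rests wholly on assumptions. That stands. In addition, w × D assumes equal on-drug response in withdrawers and continuers. If that fails, the restricted and all-values summaries will also differ because of who withdraws.

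A third reply is that cutting at the last dose date itself would discard a sample taken a day or two after the last dose, for example at the visit where treatment was stopped. That also stands, and the fix allows for it.

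A reader might also infer that the prior-1500 mg rows at Weeks 4 and 8 would consist mostly of off-drug values. SAP 2.1 says: "Participants who were treated with placebo or voxelotor 900 mg in Study GBT440-031 have additional study visits", namely at those two weeks, so most prior-1500 mg participants have no scheduled sample then. The documents do not establish that such rows will appear: SAP 4.2 gives displays by prior treatment only where appropriate, and the table shells are in a separate document. It remains a possibility to check against the shells.

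**Conclusion.** The point holds as an optional, low-impact improvement. Followed as written, the SAP mixes values taken 28-35 days off drug into the Week 4-48 durability means. If the effect wanes off drug, durability is understated, at Week 48 by about 0.005-0.12 g/dL under the stated assumptions, or roughly one third less if late EOS samples are not drawn. Transfusion replacement and unscheduled samples make the low end more likely.

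A reader might infer that the durability result is materially distorted, or made to look better than it is. The documents support neither. Waning would bias the means against the drug, no formal test is planned, and completers should be on drug at EOS. Nor are the laboratory and vital-sign safety summaries at fault for including off-drug values, because they are not meant to isolate on-treatment effect.

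**What to change.** Add one sentence to SAP 5.5: the by-visit summaries of hemoglobin, indirect bilirubin, % reticulocytes and absolute reticulocytes use samples collected up to the last dose date plus a short prespecified number of days, well below 28. The 28-day limit used in 5.3.3 would not do, because it still admits a sample taken exactly 28 days after the last dose. Apply the limit before window averaging and before the transfusion replacement. Use the same last dose date as the exposure calculation in 5.3.1. Keep the all-values summary as a sensitivity analysis, and leave 5.3.3 and 5.3.5 unchanged.

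The cost is one sentence, one programming flag and one extra table, which partly overlaps the all-values laboratory summary in 5.3.3 (that summary has no transfusion replacement). The downside is slightly fewer values per visit and a possible tilt toward participants still on drug, which the all-values summary would show. No new visits or data are needed.
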